## 6.4. Visit Windows

All assessments will be included in the listings. No visit windows will be applied to assessments.

## 6.5. Pooling of Centers

Data from all centers/sites will be pooled together.

## 7. Demographic, Other Baseline Characteristics and Medication

### 7.1. Subject Disposition and Withdrawals

Study completion and withdrawals (with reasons) will be summarized for all enrolled subjects.

Inclusion in each analysis population will be summarized, along with reasons for exclusion.

### 7.2. Demographic and Other Baseline Characteristics

Demographic and baseline characteristics (cataplexy, without cataplexy, duration of narcolepsy, baseline data of MWT, ESS, CGI-S, PGI-C) will be summarized using descriptive statistics. Demographics and informed consent data will be listed for all randomized subjects.

Age at date of informed consent= (date of informed consent- date of birth + 1) / 365.25 and truncated to complete years.

### 7.3. Medical History and Disease History

Medical history will be coded by System Organ Class (SOC) and Preferred Term (PT) using MedDRA version 22.0 (or) higher version.

Medical history will be summarized by treatment group and overall, and sorted by frequency (descending order based on overall totals) by SOC and PT.

Separate Summaries will be performed for Medical History and Disease History on the Safety Population. All available medical history information will be listed on all randomized subjects.

### 7.4. Prior and Concomitant medication

All non-study medications will be classified using the dynamic version of the World Health Organization Drug Dictionary (WHODD) coding dictionary version Global B3 March 2019 or higher version. Coding includes the Anatomical Therapeutic Chemical (ATC) classification levels 1 and 2 and preferred term.

Any medication which started before the first dose of study medication will be categorized as Prior Medication. Any medication continued or started after the first dose of study medication will be categorized as concomitant medication.

Concomitant medications will be summarized by the ATC levels and preferred term. All non-study medications will be listed.

Missing dates will not be imputed. However the following table will be utilized to categorize prior and concomitant medication.

Medication start (↑) /end (→) date	< baseline visit	≥ baseline visit	All cases where year is missing or ongoing is ticked	Month and Day is missing		Only Day is missing	
				Year of Medication < Year of baseline visit	Year of Medication ≥ Year of baseline visit	Month-Year of Medication < Month-Year of baseline visit	Month-Year of Medication ≥ Month-Year of baseline visit
< baseline visit	P	PC	PC	P	PC	P	PC
≥ baseline visit		C	C		C		C
All cases where year is missing	P	PC	PC	P	PC	P	PC
Month	Year of	P	PC	PC	P	P	PC

This document is confidential.

**Statistical Analysis Plan**

Sponsor: Suven Life Sciences; Protocol No.: CTP2S13031H3

Medication start (↓) /end (→) date		< baseline visit	≥ baseline visit	All cases where year is missing or ongoing is ticked	Month and Day is missing		Only Day is missing	
					Year of Medication < Year of baseline visit	Year of Medication ≥ Year of baseline visit	Month-Year of Medication < Month-Year of baseline visit	Month-Year of Medication ≥ Month-Year of baseline visit
and Day is missing	Medication < Year of baseline visit							
	Year of Medication ≥ Year of baseline visit	P	C	C		C	P	C
Only Day is missing	Month-Year of Medication < Month-Year of baseline visit	P	PC	PC	P	PC	P	PC
	Month-Year of Medication ≥ Month-Year of baseline visit	P	C	C		C		C

Abbreviations: P=Prior, C=Concomitant, PC=Prior and Concomitant.

This document is confidential.

## 8. Efficacy Evaluation

The primary testing approach for efficacy is the statistical comparison of the pooled active SUVN-G3031 dose groups (2 mg/day and 4 mg/day) versus placebo. Additionally, each active dose will be tested against placebo. All statistical tests will be performed at alpha=5% for the two-sided test.

## 8.1. Primary Efficacy Endpoint and Analysis (Primary Estimand)

The null ( $H_0$ ) and alternative ( $H_1$ ) hypotheses of the study are as follows:

H0: SUVN-G3031 and placebo do not differ in their change from baseline in the mean total ESS score at Day 14.

H1: SUVN-G3031 and placebo differ in their change from baseline in the mean total ESS score at Day 14.

[figure not shown]
The primary estimand is defined with the following 5 attributes:

The primary analysis approach will be performed using a mixed model repeated measures (MMRM) analysis. This model considers all observed post-baseline assessments of both post-baseline visits (Day 7 and Day 14), in case of death, the visits after the death will be filled with the worst observed value post-baseline, prior to entering the MMRM. In the MMRM all missing values will be imputed via direct likelihood based on the assumption of missing at random.

The MMRM model will include randomized treatment (for the pooled analysis, both active treatments will be combined), visit and treatment (for the pooled analysis, both active treatments will be combined) by visit interaction as explanatory variables, stratification factor for cataplexy subject history (presence or absence) and baseline MWT score as continuous covariates. An unstructured covariance structure will be assumed. Least square mean changes will be estimated for each single treatment and the difference of each SUVN-G3031 dose versus placebo. Results of comparison of pooled active treatment groups versus placebo will be presented. Additionally, the analysis will be repeated with consideration of single treatment groups.

If the assumptions underpinning the MMRM are found to be violated, either a log transform or an analysis based on ranked data will be performed as appropriate and least squares means, 95% confidence intervals, and p-values of the treatment comparisons (across visits and within visits) for descriptive purposes along with basic arithmetic summary statistics (mean, median, SD, standard error of the mean, min, and max) will be provided.

If the statistical comparison of pooled active dose group versus placebo results in superiority with p-values less or equal to 5% then SUVN-G3031 can be considered as superior to placebo in a confirmatory way. Otherwise result will be interpreted in an exploratory way.

---

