#### **14.3.1 Analysis of Primary Efficacy Endpoint**

The primary efficacy endpoint is the change from baseline in the mean total ESS score at Day 14. A successful study requires demonstration of statistically significant differences between the combined SUVN-G3031 doses (2 mg and 4 mg) group and the placebo group at endpoint for the ESS.

The null (H0) and alternative (H1) hypotheses of the study are as follows:

H0: SUVN-G3031 and placebo do not differ in their change from baseline in the mean total ESS score at Day 14.

H1: SUVN-G3031 and placebo differ in their change from baseline in the mean total ESS score at Day 14.

The primary endpoint will be analyzed using a mixed model repeated measures (MMRM) analysis that includes the mean total ESS score from baseline to 7 days through to 14 days. This method is the preferred approach to longitudinal analysis because it utilizes observed data efficiently.

The model will include randomized treatment, visit and treatment-by-visit interaction as explanatory variables, stratification factor for cataplexy patient history (presence or absence) and baseline total ESS score as covariates. The participant effect will be assumed to be random, and an unstructured covariance structure will be assumed for within participant variation. The main comparison will be a contrast between treatment groups at 14 days. Least square mean changes will be estimated for SUVN-G3031 and placebo.

This analysis will be repeated for the ITT and PP populations.

Various sensitivity analyses will be performed using an analysis of covariance (ANCOVA) and multiple imputation pattern mixture model to handle missing data. Estimands specification and sensitivity analyses details will be included in the SAP.

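### Testing the pooled effect as an equal-weight contrast from the three-arm MMRM, instead of merging 2 mg and 4 mg into one level, would be slightly more efficient and would fix the dose weights at little cost

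*SAP*

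**What the plan says.** SAP 8 sets the confirmatory comparison: "The primary testing approach for efficacy is the statistical comparison of the pooled active SUVN-G3031 dose groups (2 mg/day and 4 mg/day) versus placebo". Tests are two-sided at 5%.

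SAP 8.1 gives the model for that comparison. The treatment term is "randomized treatment (for the pooled analysis, both active treatments will be combined", and the same bracket is attached to the treatment-by-visit term, so dose is absent from the pooled model altogether. On covariance it says "An unstructured covariance structure will be assumed", and on missing data "In the MMRM all missing values will be imputed via direct likelihood based on the assumption of missing at random".

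The same section also asks for by-dose results: "Least square mean changes will be estimated for each single treatment and the difference of each SUVN-G3031 dose versus placebo", and "Additionally, the analysis will be repeated with consideration of single treatment groups". A two-level model cannot supply these, so the three-arm model will be fitted in any case.

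Protocol 14.3.1 defines success as combined doses against placebo and lists randomized treatment as a model term. It adds: "The main comparison will be a contrast between treatment groups at 14 days". It does not say whether the doses are merged in the model or averaged by a contrast. Protocol 9.3.1 sets 1:1:1 randomization. The readable text gives no weights for the two doses and no reason for merging.

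**The concern.** Merging two randomized arms in the model has two consequences.

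1. **Standard error.** If 2 mg and 4 mg truly differ, patients on each dose scatter around a pooled mean that fits neither. The model treats that scatter as residual variance and reports too large an SE.
2. **Weights and missing data.** The likelihood-based handling of missing values conditions on the variables in the model. With dose left out, a missing Day 14 value on 4 mg is in effect predicted from a mixture of both doses. The doses are then weighted by the patients who remain, not by the 1:1 randomization. The three-arm model needs the weaker assumption: missing at random given the dose received.

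This one p-value decides whether the study succeeds, and it gates both secondary endpoints (SAP 8.4), so even a small avoidable loss is worth removing.

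**Working it through.** **Inputs from the documents.** SD 5.0, effect 3.5, 10% dropout and 38 per group (Protocol 14.1, all for MWT); 57 per group after re-estimation (SAP 3.6); 1:1:1 allocation; two-sided 5%.

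**Assumed, because the documents give no value.** ESS SD 5; correlation between visits 0.6; a dose difference D of 0 to 4 points; mean effect 2 or 2.5; retention by dose as shown.

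**The plan's own figure.** A two-sample t-test with 34 evaluable per arm, difference 3.5 and SD 5 has 81.2% power; 34/0.9 = 37.8, so 38 per group. This reproduces the plan. It concerns one arm against placebo on MWT, so it neither supports nor contradicts the point.

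**SE.** Two thirds of patients are on active drug, each dose lying D/2 from the pooled mean. The residual variance becomes s² + (2/3)(D/2)² = s² + D²/6, so the reported SE is multiplied by √(1 + D²/(6s²)). With s = 5:
- D = 2: √(1 + 4/150) = 1.013
- D = 3.5: √(1 + 12.25/150) = 1.040
- D = 4: √(1 + 16/150) = 1.052

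**Weights.** From completers alone, the shift is D × (n_a/(n_a + n_b) − 1/2). With 95% and 80% retained, 0.95/1.75 = 0.543, so the shift is 0.043 × D: 0.09 points at D = 2, 0.15 at 3.5, 0.17 at 4. Day 7 data in the MMRM recover roughly half of this. They cannot do so for patients with no post-baseline ESS, whom the ITT definition excludes.

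**Two-visit unstructured model, simulated at 57 per arm.** Mean effect is the size of the average ESS reduction against placebo. There were 4,000 trials per case at mean effect 2 and 8,000 at 2.5; the Monte Carlo SE of one power figure at 4,000 trials is √(0.68 × 0.32/4000), about 0.7 points.

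| Mean effect | D | Day 14 retention, placebo/2 mg/4 mg | Estimate, merged / contrast | Power, merged / contrast |
|---|---|---|---|---|
| 2 | 0 | full | – | 68.6% / 68.7% |
| 2 | 2 | full | – | 68.1% / 69.2% |
| 2 | 4 | full | – | 65.0% / 68.8% |
| 2 | 0 | 95/95/80% | – | 64.9% / 64.9% |
| 2 | 2 | 95/95/80% | 1.96 / 2.01 | 63.4% / 66.6% |
| 2 | 4 | 95/95/80% | 1.90 / 2.00 | 58.1% / 66.5% |
| 2.5 | 3.5 | 90/90/90% | 2.51 / 2.51 | 81.9% / 83.7% |
| 2.5 | 2 | 90/95/80% | 2.46 / 2.51 | 81.3% / 83.2% |
| 2.5 | 3.5 | 90/95/80% | 2.44 / 2.51 | 79.5% / 83.8% |

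In every row with D above 0, 4 mg is the stronger dose. At D = 3.5 with 90% retained in each arm, the merged model reports an SE of 0.879 against an actual SD of 0.836; the contrast reports 0.846 against 0.835.

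**If the true effect is near 3.5** (closed form, Day 14 data only, 57 per arm). Merged against contrast, without dropout: 99.0% against 99.0% at D = 2 and 98.7% against 99.0% at D = 4. With 95/95/80% retention: 98.0% against 98.5% and 96.9% against 98.5%.

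**Opposite direction** (same closed form, mean effect 2). If the weaker dose is the one with 80% retention, merged power is 68.1% against 65.2% at D = 2 and 69.1% against 65.2% at D = 4. That gain comes from bias away from zero.

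**Type I error.** With D = 3.5, a zero average effect and 90% retained in each arm, the rejection rate is 4.2% merged and 4.8% with the contrast.

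**Cost of the contrast if the doses are equal.** The SE rises by 0.05% at 95/85% retention by dose, 0.13% at 95/80% and 0.41% at 95/70%, and not at all at equal retention. One fewer residual degree of freedom at Day 14 moves the critical value from 1.9760 to 1.9761.

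**The case against.** The strongest reply is that nothing is broken. The protocol makes the combined-dose group the basis of success, and a two-level factor with a Day 14 contrast satisfies that wording. If neither dose works, merging is the correct model; if the doses differ, the test errs on the conservative side. All of this stands. A reader might infer that the SAP contradicts the protocol, or that the primary test is invalid; the documents support neither.

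The size also depends on assumptions. No document gives an ESS effect of 2 or dropout that differs by dose. Protocol 5.2.2 reports no discontinuations for adverse events in Phase 1 (healthy volunteers), and Protocol 8.4 asks patients who withdraw at a visit while still on drug to complete that visit's assessments. A reader might infer a loss of about 12 power points: Day 14 data alone give 54% against 66% at mean effect 2, D = 4 and 95/95/80% retention. The planned model also uses Day 7, and that case assumes 2 mg does nothing. Nor can one say that merging biases the result toward zero: the direction depends on which dose keeps its patients.

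Two further objections stand in part. The CHW interval in SAP 11.2 uses a pooled variance and two sample sizes, so the change is more than one line of code. The sample size has already been raised after an unblinded interim, so a change of estimator now needs care; Protocol 14.6 confines those results to the DMC and its statistician, and fixed weights do not depend on data. By-dose estimates will show a dose difference if there is one, but they do not alter the confirmatory test.

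The estimand attributes, SAP 8.2 and 8.3, and the appendix code cannot be read. A contrast or weights may be defined there; if so, 8.1 needs only to agree with them.

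**Conclusion.** A cheap improvement in efficiency and in clarity about what is estimated, not a fault in validity. Merging overstates the SE by 1.3% to 5.2% for dose differences of 2 to 4 points at an assumed ESS SD of 5. It replaces equal dose weights by retention weights, a shift of about 0.05 to 0.10 points for those differences at 95% and 80% retention in the two-visit model.

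The power loss is about 1 to 4 points without differential dropout at a mean effect of 2. It is about 2 to 8 points in the simulated cases where the stronger dose retains fewer patients, and negligible near an effect of 3.5 (at most 1.6 points, in the most adverse case computed). If the doses are equal, there is essentially nothing to gain or lose. The SE result needs only a dose difference; the shift needs both effect and retention to differ by dose.

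**What to change.** - In SAP 8.1, state before final unblinding that the primary pooled effect is the Day 14 contrast (1/2, 1/2, −1) of 2 mg, 4 mg and placebo from the three-arm treatment-by-visit MMRM. Take the by-dose differences from the same fit.
- In SAP 11.2, use that contrast and its SE for both stage-wise statistics. Restate the interval constant to match: S from the three-arm model, and √(1/n_P + 1/(4n_2mg) + 1/(4n_4mg)) in place of the two-group term. When the two doses have equal numbers n, the dose terms sum to 1/(2n), as in the two-group formula.
- Apply the same contrast to CGI-S and MWT.
- Record that the change was made by staff without access to the interim results.

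The cost is two extra model parameters, an SE up to about 0.4% larger in the cases tried if the doses are equal and retention is not, and a minor restatement of the CHW formulas. No new data or additional model is needed.

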#### 8.4. Secondary Efficacy Endpoint(s) and Analyses (Secondary Estimands)

The secondary efficacy endpoints for this study are:

- Change from baseline in the mean CGI-S score related to EDS at Day 14
- Change from baseline in the mean MWT score at Day 14

The two secondary estimands investigate the efficacy endpoints 'Difference to placebo in the change from baseline in the CGI-S score related to EDS at Day 14' on the ITT population using a MMRM analysis, and the 'Difference to placebo in the Change from baseline in the MWT score at Day 14' on the ITT population using a MMRM analysis. MMRM considers all observed post-baseline assessments of both post-baseline visits (Day 7 and Day 14), , in case of death, the visits after the death will be filled with the worst observed value post-baseline from all subjects, prior to entering the MMRM In the MMRM all missing values will be imputed via direct likelihood based on the assumption of missing at random.

The approaches to handle intercurrent events for secondary endpoints will be consistent with those for the primary endpoint.

The testing of secondary endpoints will be controlled using hierarchical testing methods. The testing of the first secondary efficacy endpoint will be performed in a confirmatory way only, if for the primary efficacy of pooled treatment is significant versus placebo. The confirmatory testing approach will proceed to the second secondary efficacy endpoint only, if pooled active treatment comparison versus placebo is significant for the first secondary efficacy endpoint. Otherwise the results will be considered as exploratory only.

The secondary endpoints will be analyzed similar to the primary efficacy endpoint: using MMRM with multiple imputation and an ANCOVA of Day 7 and Day 14 data with multiple imputation as sensitivity analyses, and by repeating the analyses on PP as supportive analyses.

The time course (Baseline, Day 7, Day 14) of mean values of CGI-S and MWT, respectively, together with +/- standard error of mean will be presented in figures for the ITT and PP populations.

Summary tables by visit by treatment with actual and changes from baseline (if applicable) will be provided for the ITT and PP population.

## **8.5. Analysis of Exploratory Endpoints**

Summary tables with actual and changes from baseline (if applicable) will be provided for the continuous exploratory endpoints (listed below), and they will be analyzed in a similar fashion as the primary endpoint, i.e., an MMRM using the ITT population and PP population. No imputations will be applied in the analysis of exploratory endpoints except total ESS score at Day 7, CGI-S score at Day 7 and MWT score at Day 7.

- Change from baseline in the mean total ESS score at Day 7
- Change from baseline in the mean CGI-S score related to EDS at Day 7
- Change from baseline in the mean MWT score at Day 7
- Change from baseline in the behavior of Sleep Diary parameters at Day 7 and Day 14 (7-day average)
- Changes in the behavior of the nocturnal overnight PSG assessments at Day 7 and Day 14
- Change in MWT score, within each of the 4 MWT sessions within a single day (Day 7 and Day 14)

Frequency tables will be provided. For binary assessments (listed below), a repeated measures responder analyses will use a generalized estimating equations with a logit link function and starting with an unstructured working correlation matrix. No imputations will be applied in the analysis of below endpoints.

- The proportion of subjects reporting CGI-C scores of 1 or 2 at Day 7 and Day 14 (EDS)
- Proportion of subjects reporting CGI-C scores of 1 or 2 or 3 at Day 7 and Day 14 (EDS)
- The proportion of subjects reporting CGI-S scores related to EDS of 1 or 2 at Day 7 and Day 14
- Proportion of subjects reporting CGI-S scores related to EDS of 1 or 2 or 3 at Day 7 and Day 14
- Proportion of subjects with improvement in the PGI-C score from baseline to Day 7 and Day 14
- Analysis of all endpoints (except Sleep Diary parameters and nocturnal overnight PSG assessments) evaluating SUVN-G3031 2 mg or 4 mg compared with placebo.

Factors included in the model will be treatment group, a stratification factor for cataplexy subject history, visit, treatment-by-visit interaction, and baseline value as a covariate. Model estimates will be based on Wald statistics.

**Statistical Analysis Plan**

Sponsor: Suven Life Sciences; Protocol No.: CTP2S13031H3

---

Sleep diary and measures collected as part of the nocturnal overnight PSG assessments at Day 7 and Day 14 will be summarized using descriptive statistics.

Further exploratory analyses will include each individual MWT session throughout the day in comparison to matched baseline sessions (morning, afternoon, or evening testing periods as defined within the protocol).

## **9. Analysis of Pharmacokinetics**

Individual SUVN-G3031 plasma concentrations versus time at pre-dose on baseline (day 0), at pre-dose and post dose ( $3 \pm 0.5$  h) on day 7 day 14 will be summarized versus time points of collection and by treatment dose using descriptive statistics of the PK profile.

The following descriptive statistics (number of subjects, arithmetic and geometric mean, SD, % coefficient of variation, % Geometric coefficient of variation, minimum, maximum, and median) of the plasma concentrations versus time will also be presented on PK population.

The concentration data will also be listed by time points of collection.

### **Figures:**

Summarized (Mean  $\pm$  SD, N) SUVN-G3031 plasma concentrations versus time at pre-dose on baseline (day 0), at pre-dose and post dose ( $3 \pm 0.5$  h) on day 7 and day 14 by treatment will be presented on a linear scale.

Summarized (Mean  $\pm$  SD, N) SUVN-G3031 plasma concentrations versus time at pre-dose on baseline (day 0), at pre-dose and post dose ( $3 \pm 0.5$  h) on day 7 and day 14 by treatment will be presented on a log scale.

## 10. Safety Evaluation

The population used for safety analyses will be the Safety Population. Safety will be assessed on the basis of adverse event (AE), clinical laboratory data, ECG parameters, physical examinations, vital signs, and C-SSRS.

Partial or missing dates of safety data will be imputed according to the most conservative approach.

The imputation would be applicable to only assigning the event. Eg. If AE start date is incomplete then date or month will be imputed just to assign if AE is treatment emergent or not. In listing all incomplete or partial dates will be presented and not imputed.

